6.1.2 Guidelines for continuation of treatment

For guidelines for continuation of treatment, refer to [Section 6.3](#) Dosing modifications.

Patients who permanently discontinue one of the study drugs for any reason other than disease progression may continue the other study drug as part of the trial therapy at the investigators discretion until disease progression, unacceptable toxicity, death or discontinuation from study treatment due to any other reason and should follow the protocol safety and efficacy assessments as scheduled. After discontinuing all study treatment, further treatment is left to the physician's discretion.

6.1.3 Ancillary treatments

Not applicable

6.1.4 Rescue medication

Not applicable

6.1.5 Treatment duration

Patients will be treated until disease progression (radiologically documented according to RECIST 1.1) or until discontinuation of study treatment due to any other reason.

6.2 Dose escalation guidelines

Not applicable.

6.3 Dose modifications

6.3.1 Dose modification and dose delay

For patients who do not tolerate the protocol-specified dosing schedule, dose adjustments are permitted in order to allow the patient to continue the study treatment. These changes must be recorded on the Dosage Administration Record CRF.

6.3.1.1 Fulvestrant

The established clinical dose of fulvestrant (500 mg) will be used in each arm and no dose modification of fulvestrant is planned in this study. For information on fulvestrant and management of related AEs refer to the Faslodex® SmPC or local Prescribing Information.

6.3.1.2 Alpelisib/placebo

Management of severe or intolerable adverse reactions requires dose reduction, temporary interruption, and/or discontinuation of alpelisib therapy. A maximum of 2 dose reductions will be allowed, after which the patient will be discontinued from treatment with alpelisib/placebo. Dose reduction should be based on the worst preceding toxicity.

Please refer to [Table 6-2](#) and [Table 6-3](#) for guidance.

Table 6-2 Dose reduction sequential steps for alpelisib/placebo

Alpelisib/placebo dose level	Dose and schedule	Number of tablets & strength
Starting dose	300 mg/day continuously	1 x 200 mg tablet and 2 x 50 mg tablet
Dose level -1	250 mg/day continuously	1 x 200 mg tablet and 1 x 50 mg tablet
Dose level -2	200 mg/day continuously	1 x 200 mg tablet

Recommendations for dose reduction or dose interruption of alpelisib/placebo in the management of adverse reactions are summarized in [Table 6-3](#). No dose modification for fulvestrant is permitted. Clinical judgment of the treating physician, including confirmation of lab values if deemed necessary, should guide the management plan of each patient based on individual benefit/risk assessment.

However, treatment must be discontinued as indicated in [Table 6-3](#).

After treatment is resumed at a lower dose:

- If the same toxicity recurs with the same severity, then the next treatment re-initiation must resume at a lower dose irrespective of duration.
- Once the alpelisib/placebo dose has been reduced, no re-escalation will occur, even upon resolution of AE.

If a patient requires a dose delay of alpelisib/placebo for > 28 days from the intended day then the patient must be discontinued from alpelisib/placebo, but may continue on fulvestrant. All scheduled assessments will continue to be performed. If fulvestrant is held for more than 35 days since a planned injection, then fulvestrant should be permanently discontinued. The patient may continue on alpelisib/placebo at the discretion of the investigator until study completion, in which case all scheduled assessments will continue to be performed.

Table 6-3 Criteria for interruption and re-initiation of alpelisib/placebo treatment

Dose Modifications for alpelisib/placebo as specified below. Fulvestrant may be continued while alpelisib/placebo dose is being held, at the investigators discretion, and as specified in Section 6.3.1	
Worst toxicity -CTCAE Grade (value)	Dose Modifications for alpelisib/placebo
Investigations (Fasting Plasma Glucose)	
Hyperglycemia (see also Section 6.3.2.1.3)	
	
Always consider consultation with a diabetologist and recommend/reinforce on lifestyle changes as per ADA, i.e. exercise and dietary advice (e.g. small frequent meals, low carb, high fiber, low process food intake, three macronutrient balanced meals and 2 optional small snacks rather than one large meal).
 
Note: this table provides dose management recommendations. The preferred option for treating alpelisib-induced hyperglycemia is metformin, given its wide availability and well characterized safety profile. However, in case of intolerance to or unavailability of metformin, investigator's judgment should be exercised and other insulin sensitizers such as SGLT2 inhibitors, thiazolidinediones or dipeptidyl peptidase-4 Inhibitors can be used.

Grade 1 (> ULN - 160 mg/dL) [> ULN - 8.9 mmol/L] For patients with baseline values between >ULN – 140 mg/dL (ULN – 7.7 mmol/L) this apply only for values > 140 mg/dL (7.7 mmol/L)	
Maintain dose level, and remind patient on lifestyle changes*.
 
 ● If FPG < 140 mg/dl, consider adding metformin as per guidance below or in cooperation with diabetologist ● If FPG 140-160 mg/dl, start/intensify metformin as per guidance below or in cooperation with diabetologist 
Metformin 500 mg once daily with dinner. If no gastrointestinal (GI) intolerance after several days, increase to 500 mg bid, with breakfast and dinner. If tolerated, increase to 500 mg with breakfast, and 1000 mg with dinner. If tolerated, 1000 mg bid with breakfast and dinner. If not tolerated, reduce to prior tolerated dose.
 
Monitor FPG as clinically indicated and at least weekly for 8 weeks, then continue checking at least every two weeks until FPG is within baseline values.

Grade 2 (>160 - 250 mg/dL) [> 8.9 - 13.9 mmol/L]	
Maintain dose level and remind patient on lifestyle changes*, exclude confounding factors like e.g. urinary tract infection, consider consultation with a diabetologist and start oral-antidiabetic treatment, e.g. metformin 500 mg bid with breakfast and dinner. If no GI intolerance, increase to 500 mg with breakfast, 1000 mg with dinner. If tolerated, 1000 mg bid with breakfast and dinner. If not tolerated, reduce to prior tolerated dose. Titrate to the maximum tolerated dose over a period of 3 weeks. A second oral hypoglycemic agent may be initiated if needed.
 
If FPG is still rising on maximum tolerated dose of metformin or persistently >160mg/dl (>8.9 mmol/L, add an SGLT2 inhibitor if available, e.g. empagliflozin up to 25 mg (max. dose). Alternatively, an insulin-sensitizer, e.g. pioglitazone 30 mg (max. dose) can be added.
 
Monitor FPG as clinically indicated and at least weekly until FPG resolves to ≤ Grade 1
 
 ● If FPG does not resolve to ≤ Grade 1 within 21 days after institution of appropriate anti-diabetic treatment, reduce alpelisib/placebo by 1 dose level ● Continue with anti-diabetic treatment and check FPG at least weekly for 8 weeks, then continue checking at least every 2 weeks, alert treating physician if FPG>250mg/dl

Dose Modifications for alpelisib/placebo as specified below. Fulvestrant may be continued while alpelisib/placebo dose is being held, at the investigators discretion, and as specified in Section 6.3.1	
Worst toxicity -CTCAE Grade (value)	Dose Modifications for alpelisib/placebo
Grade 3 (FPG > 250 - 500 mg/dL) [> 13.9 - 27.8 mmol/L]	
Omit alpelisib/placebo and confirm fasting status of the assessment. If non-fasting, re-check within 24 hours.
 
Regardless of fasting status, consider IV fluids if symptoms of hyperglycemia or signs of volume depletion.
 
Exclude confounding factors like e.g. urinary tract infection and consider consultation with a diabetologist.
 
Administer intravenous hydration and intervention for electrolyte/ketoacidosis/hyperosmolar disturbances as clinically appropriate. Start metformin and titrate as outlined for Grade 2, add insulin sensitizers (i.e. pioglitazone) or a SGLT2 inhibitor, if available, as outlined for Grade 2. Insulin may be used for 1-2 days until hyperglycemia resolves, however this may not be necessary in the majority of alpelisib-induced hyperglycemia given the short half-life of alpelisib.
 
Monitor FPG as clinically indicated and at least twice weekly until FPG resolves to \leq Grade 1.
 
 • If FPG resolves to \leq 160 mg/dL within 3-5 days, while off study treatment and on metformin, re-start alpelisib/placebo and reduce 1 dose level, continue with anti-diabetic treatment..A second and third oral hypoglycemic agent may be initiated concomitantly, if needed, in consultation with a diabetologist. Check FPG at least weekly for 8 weeks, then continue checking at least every 2 weeks, alert treating physician if FPG>250mg/dl • If FPG does not resolve to \leq 160 mg/dL within 3-5 days while off study treatment and on metformin, consult a diabetologist for management of diabetes is strongly recommended. • If FPG does not resolve to \leq 160 mg/dL within 21 days after institution of appropriate anti-diabetic treatment in cooperation with diabetologist and exclusion of confounding factors e.g. urinary tract infection, permanently discontinue patient from alpelisib/placebo treatment.
Grade 4 (FPG > 500 mg/dL) [≥ 27.8 mmol/L]	
Omit alpelisib/placebo, confirm fasting status of the assessment. If non-fasting, re-check within 24 hours.
 
 • Regardless of fasting status, consider IV fluids. Exclude confounding factors like e.g. urinary tract infection. • Should consult with diabetologist, initiate or intensify medication with appropriate anti-diabetic treatment (see Grade 3), re-check within 24 hours. • If grade improves then follow specific grade recommendations • If FPG is confirmed at Grade 4 and confounding factors could be excluded, permanently discontinue patient from alpelisib/placebo.

Dose Modifications for alpelisib/placebo as specified below. Fulvestrant may be continued while alpelisib/placebo dose is being held, at the investigators discretion, and as specified in Section 6.3.1	
Worst toxicity -CTCAE Grade (value)	Dose Modifications for alpelisib/placebo
A diabetologist consultation should always be considered. For all grades : instruct patient to follow dietary guidelines according to local and/or institutional standards for management of diabetes mellitus (such as those provided by the American Diabetes Association) during the study, e.g. controlled carbohydrate intake, high fiber, low processed food intake; three macronutrient balanced meals and 2 small snacks rather than one large meal.	
* specific recommendations please see Section 6.3.2.1.3 .	
Thrombocytopenia	
Grade 1 (PLT < LLN - $75 \times 10^9/L$)	Maintain dose level
Grade 2 (PLT < $75 - 50 \times 10^9/L$)	
Grade 3 (PLT < $50-25 \times 10^9/L$)	Omit dose until resolved to \leq Grade 1, then: 
 • If resolved in \leq 7 days, then maintain dose level • If resolved in $>$ 7 days, then \downarrow 1 dose level
Grade 4 (PLT < $25 \times 10^9/L$)	Omit dose until resolved to \leq Grade 1, then \downarrow 1 dose level
Investigations (Renal)	
Serum creatinine	
< 2 x ULN	Maintain dose level
2 – 3 x ULN	Omit dose until resolved to \leq grade 1, then: 
 • If resolved in \leq 7 days, then maintain dose level • If resolved in $>$ 7 days, then \downarrow 1 dose level
Grade 3 (> 3.0 – 6.0 x ULN)	Permanently discontinue patient from alpelisib/placebo
Grade 4 (> 6.0 x ULN)	Permanently discontinue patient from alpelisib/placebo
Investigations (Hepatic)	
Isolated total Bilirubin elevation	
Grade 1 (> ULN - $1.5 \times$ ULN)	No dose adjustment is required. Initiate appropriate medical therapy and monitor as clinically indicated.
Grade 2 (> $1.5 - 3.0 \times$ ULN)	Omit dose until resolved to \leq Grade 1, then: 
 • If resolved in \leq 14 days, then maintain dose level • If resolved in $>$ 14 days, then \downarrow 1 dose level
Grade 3 (> $3.0 - 10.0 \times$ ULN)*	Interrupt dose until recovery to Grade \leq 1, then resume at the next lower dose level.
Grade 4 (> $10.0 \times$ ULN)*	Permanently discontinue patient from alpelisib/placebo
Isolated AST or ALT Elevation	
Grade 1 (> ULN – $3.0 \times$ ULN)	Maintain dose level. Initiate appropriate medical therapy and monitor as clinically indicated.
Grade 2 (> $3.0 - 5.0 \times$ ULN)	No dose adjustment is required. Initiate appropriate medical therapy and monitor as clinically indicated.

Dose Modifications for alpelisib/placebo as specified below. Fulvestrant may be continued while alpelisib/placebo dose is being held, at the investigators discretion, and as specified in Section 6.3.1	
Worst toxicity -CTCAE Grade (value)	Dose Modifications for alpelisib/placebo
Grade 3 (> 5.0 - 20.0 x ULN) •	Interrupt dose until recovery to Grade ≤ 1, then resume at the next lower dose level. •
Grade 4 (> 20.0 x ULN) •	Permanently discontinue.
Combined ^a elevations of AST or ALT and total Bilirubin	Please see specific instructions in Section 6.3.2.1.5
	•
All dose modifications should be based on the worst preceding toxicity.	
^a "Combined" defined as total bilirubin increase to the defined threshold concurrently with ALT/AST increase to the defined threshold	
If combined elevations of AST or ALT and total bilirubin do not meet the defined thresholds, please follow the instructions for isolated elevation of total bilirubin and isolated elevation of AST/ALT, and take a conservative action based on the degree of the elevations (e.g. discontinue treatment at the situation when omit dose is needed for one parameter and discontinue treatment is required for another parameter). After all elevations resolve to the defined thresholds that allow treatment re-initiation, re-start the treatment either at the same dose or at one dose lower if meeting a criterion for dose reduction	
* Note: If total bilirubin > 3.0 x ULN is due to the indirect (non-conjugated) component only, and hemolysis as the etiology has been ruled out as per institutional guidelines (e.g. review of peripheral blood smear and haptoglobin determination), then ↓ 1 dose level and continue treatment at the discretion of the investigator.	

Dose Modifications for alpelisib/placebo as specified below. Fulvestrant may be continued while alpelisib/placebo dose is being held, at the investigators discretion, and as specified in Section 6.3.1	
Worst toxicity -CTCAE Grade (value)	Dose Modifications for alpelisib/placebo
Investigations (Cardiac)	
Cardiac – QTc prolongation	
QTcF > 500 ms (\geq Grade 3) or > 60 ms change from baseline on at least two separate ECGs	
First Occurrence:
 
 1. Assess the quality of the ECG recording and the QT value and repeat if needed 2. Interrupt study treatment 3. Determine the serum electrolyte levels (in particular hypokalemia, hypomagnesemia). If abnormal, correct abnormalities before resuming study drug treatment. 4. Review concomitant medication use for other causes for QT prolongation (refer to crediblemeds.org for known QT prolonging drugs), and for drugs with the potential to increase the risk of drug exposure related QT prolongation 5. Check study drug dosing schedule and treatment compliance 6. Consider collecting a time-matched PK sample and record time and date of last study drug intake. 
After confirming ECG reading at site, if QTcF > 500 ms or > 60 ms change from baseline
 
 • Interrupt study treatment • Repeat ECG and confirm ECG diagnosis by a cardiologist 
If QTcF confirmed > 500 ms or > 60 ms change from baseline
 
 • Correct electrolytes, eliminate culprit concomitant treatments, and identify clinical conditions that could potentially prolong the QT • Consult with a cardiologist (or qualified specialist) • Increase cardiac monitoring as indicated, until the QTcF returns to \leq 480 ms or < 60ms change from baseline. • After resolution to \leq 480 ms /60 ms change from baseline, consider re-introducing treatment at reduced dose, and increase ECG monitoring • If QTcF remains \leq 500 ms/60 ms change from baseline after dose reduction, continue planned ECG monitoring during subsequent treatment • If QTcF recurs > 500 ms/60 ms change from baseline after dose reduction, discontinue patient from alpelisib/placebo.
Cardiac - Left Ventricular Systolic Dysfunction	
Asymptomatic, resting ejection fraction 40-50%; or 10-20% drop from baseline	
 -Maintain dose level, and continue alpelisib with caution -Repeat LVEF within 4 weeks or as clinically appropriate
Symptomatic, responsive to intervention, ejection fraction 20-39% or > 20% drop from baseline	
 -Omit alpelisib/placebo until resolved* (as defined below), then \downarrow 1 dose level -LVEF measurement to be repeated, if not resolved* within 28 days permanently discontinue patient from alpelisib/placebo treatment
Refractory or poorly controlled, ejection fraction < 20%	Permanently discontinue patient from alpelisib/placebo
<small>*the event is considered resolved when the patient is asymptomatic, has a resting ejection fraction \geq 40% and \leq 20% decrease from baseline.</small>	

Dose Modifications for alpelisib/placebo as specified below. Fulvestrant may be continued while alpelisib/placebo dose is being held, at the investigators discretion, and as specified in Section 6.3.1	
Worst toxicity -CTCAE Grade (value)	Dose Modifications for alpelisib/placebo
Other Cardiac Events	
Grade 1 or 2	Maintain dose level
Grade 3	Omit dose until resolved to \leq Grade 1, then \downarrow 1 dose level
Grade 4	Permanently discontinue patient from alpelisib/placebo
Investigations (Gastrointestinal)	
Diarrhea (see also Appendix 4)	
Grade 1	Maintain dose level but initiate appropriate medical therapy and monitor as clinically indicated
Grade 2	Omit dose until resolved to \leq Grade 1, then restart at same dose If diarrhea returns as \geq Grade 2, then omit dose until resolved to \leq Grade 1, then decrease 1 dose level
Grade 3	Omit dose until resolved to \leq Grade 1, then \downarrow 1 dose level Manage according to local standard of care medical management, including electrolyte monitoring, administration of antiemetics and antidiarrhoeal medicinal products and/or fluid replacement and electrolyte supplements, as clinically indicated
Grade 4	Discontinue patient from treatment. Manage according to local standard of care medical management, including electrolyte monitoring, administration of antiemetics and antidiarrhoeal medicinal products and/or fluid replacement and electrolyte supplements, as clinically indicated.
Investigations (Pancreatic)	
Pancreatitis	
Grade 2 (enzymatic elevation or radiologic findings only)	Omit dose until resolved to Grade \leq 1, then resume treatment at \downarrow 1 dose level. If toxicity recurs, permanently discontinue patient from alpelisib/placebo
Grade 3	
 For patients deriving clinical benefit upon investigator's judgement: 
 Omit dose until complete resolution of symptoms and lipase resolved to Grade \leq 1, then resume treatment at \downarrow 1 dose level. Only 1 dose reduction is allowed. 
 If recovery to \leq Grade 1 is greater than 28 days, the patient must be discontinued from the study. If toxicity reoccurs, permanently discontinue patient from alpelisib/placebo Permanently discontinue patient from alpelisib/placebo
Grade 4	Permanently discontinue patient from alpelisib/placebo
Stomatitis/Oral mucositis (see also Appendix 5)	
Grade 1/Tolerable Grade 2	Maintain dose level. Non-alcoholic or salt water mouth wash.
Intolerable Grade 2 or Grade 3	First occurrence: hold until \leq Grade 1 and \downarrow 1 dose level (if stomatitis is readily manageable with optimal management, re-introduction at the same level might be considered at the discretion of the investigator). Second occurrence: hold until \leq Grade 1 and \downarrow 1 dose level.
Grade 4	Permanently discontinue patient from alpelisib/placebo.

Dose Modifications for alpelisib/placebo as specified below. Fulvestrant may be continued while alpelisib/placebo dose is being held, at the investigators discretion, and as specified in Section 6.3.1	
Worst toxicity -CTCAE Grade (value)	Dose Modifications for alpelisib/placebo
Skin and subcutaneous tissue disorders	

Consultation with a dermatologist is highly recommended for better assessment and management of alpelisib-induced skin toxicity. (see also Section 6.3.2.1.2). Dermatologist consultation is mandated for serious cutaneous reactions (i.e. fulfilling seriousness criteria for AE Reporting) and for severe cutaneous reactions like Stevens-Johnson-Syndrome, Toxic Epidermal Necrolysis, Erythema Multiforme, Drug Reaction with Eosinophilia and Systemic Symptoms (DRESS)
	
Rash	
Grade 1 (<10% body surface area (BSA) with active skin toxicity*)	
Maintain dose level
 
 Initiate topical corticosteroids 3-4 x daily, preferred compounds to use are Triamcinolone, Betamethasone as long as skin toxicity is active, during maximum 28 days 
If active rash is not resolved within 28 days of appropriate treatment, add low dose systemic corticosteroid (20-40 mg/d), such as prednisone 10 mg 3x/day.
 
For patients with symptoms like burning and/or pruritus add non-sedating anti-histamine, such as cetirizine once daily during daytime and a sedating anti-histamine such as diphenhydramine once daily at night

Grade 2 (10-30% BSA with active skin toxicity*)	
Maintain dose level.
 
 Initiate or intensify topical corticosteroids 3-4x daily, preferred compounds to use are Triamcinolone or Betamethasone as long as skin toxicity is active, up to max. 28 days Add systemic corticosteroids 20-40mg/d 
If rash resolves to ≤ G1 within 10 days systemic corticosteroid may be discontinued. For patients with symptoms like burning, stinging and/or pruritus add non-sedating anti-histamine, such as cetirizine once daily during daytime and a sedating anti-histamine such as diphenhydramine once daily at night

Grade 3 (>30% BSA with active skin toxicity*)	
Omit alpelisib/placebo dose until rash /skin toxicity is improved to Grade 1 or resolved, recommend documentation by photography and consider performing a skin biopsy.
 
Initiate topical corticosteroids 3-4x daily, preferred compounds to use are Triamcinolone or Betamethasone for at least 28 days
 
Add systemic corticosteroids 20-40mg/d
 
If rash resolves to ≤ G1 within 10 days systemic corticosteroid may be discontinued
 
Re-start alpelisib/placebo dose once rash /skin toxicity is no longer active but fading (G1):
 
 - at a reduced dose in case of first occurrence, - If rash/skin toxicity still active in up to 10% BSA after more than 14 days, continue oral corticosteroid for at least 48 hours upon re-challenge with alpelisib/placebo; if rash and/or pruritus do not reoccur within 48 hours after re-challenge with alpelisib, systemic corticosteroid may be discontinued 
For patients with symptoms like burning, stinging and/or pruritus add a non-sedating anti-histamine such as cetirizine once daily during daytime and a sedating anti-histamine such as diphenhydramine once daily at night. Antihistamine regimen should be continued for a minimum of 28 days after re-challenge with alpelisib/placebo.

Dose Modifications for alpelisib/placebo as specified below. Fulvestrant may be continued while alpelisib/placebo dose is being held, at the investigators discretion, and as specified in Section 6.3.1	
Worst toxicity -CTCAE Grade (value)	Dose Modifications for alpelisib/placebo
Grade 4 (any % BSA associated with extensive superinfection, with IV antibiotics indicated; life-threatening consequences)	
Permanently discontinue patient from alpelisib/placebo
 
Consult a dermatologist, ensure documentation by imaging like photographs, and obtain a skin biopsy
 
Treatment may follow guidelines for Grade 3 above with the exception of rechallenge .
 
Additional measures may be taken as per local treatment guidance.
 
 •
Any Grade of Stevens-Johnson-Syndrome /Toxic Epidermal Necrolysis/Drug Reaction with Eosinophilia and Systemic Symptoms (DRESS) or other SJS/TEN/DRESS like severe skin reactions	
Permanently discontinue patient from alpelisib/placebo
 
Consult a dermatologist, ensure documentation by imaging like photographs, and obtain a skin biopsy
 
Follow local treatment guidelines for SJS/TEN/ DRESS

**Active" skin toxicities: If there are no new lesions or new areas of involvement developing, and if lesion appearance is changing color from red to pale or light brown, it is likely the skin toxicity has begun to fade and is not to be considered "active" any longer. Treatment reduction can be considered for these areas. The appearance of skin toxicity may fade slowly, over 10 days or more but not requiring ongoing therapy.	
Immune system disorders	
Hypersensitivity	
Please see specific instructions in Section 6.3.2.1.6	
Investigations (Pulmonary disorders)	
Pneumonitis	
Please see specific instructions in Section 6.3.2.1.1 .	
Investigations (Metabolic)	
Asymptomatic amylase and/or lipase elevation (see also Section 6.3.2.1.4)	
Grade 1 (> ULN - 1.5 x ULN)	Maintain dose level
Grade 2 (> 1.5 - 2.0 x ULN)	Maintain dose level
Grade \geq 3 (> 2.0 x ULN)	
Omit dose until resolved to baseline, then
 
 • If resolved in \leq 14 days, maintain dose level • If resolved in $>$ 14 days, then \downarrow 1 dose level. 
Note:
 
 • In cases of isolated amylase elevations only, dosing may be maintained provided amylase fractionation demonstrates that pancreatic amylase is \leq Grade 1. Monitor total amylase (and continue to assess fractionated amylase) as specified in Section 6.3.2.1.4.
Note: Withhold study treatment for acute onset of new or progressive unexplained abdominal symptoms, such as severe pain or vomiting; and perform diagnostic procedures (e.g. abdominal CT scan or ultrasound) to exclude pancreatic pathology.	
Investigations (any other)	
Other adverse events	
Grade 1 or 2	Maintain dose level
Grade 3	Omit dose until resolved to \leq grade 1, then \downarrow 1 dose level
Grade 4	
Permanently discontinue from alpelisib/placebo
 
Omit dose for \geq grade 3 vomiting or grade 3 nausea only if the vomiting or nausea cannot be controlled with optimal antiemetic (as per local practice)

Dose Modifications for alpelisib/placebo as specified below. Fulvestrant may be continued while alpelisib/placebo dose is being held, at the investigators discretion, and as specified in Section 6.3.1	
Worst toxicity -CTCAE Grade (value)	Dose Modifications for alpelisib/placebo
For additional details on the safety profile of alpelisib, please refer to the alpelisib Investigator Brochure.	

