2.6 Risks and benefits

2.6.1 Potential benefit for participants

Treatment with alpelisib in combination with fulvestrant may result in an improved clinical benefit compared to fulvestrant alone in men and postmenopausal women with HR+, HER2-

negative advanced breast cancer, which progressed on or after AI treatment. All patients enrolled in this trial will receive an active endocrine therapy for their disease (see [Section 2.5](#)). Based on preclinical and preliminary clinical data (see [Section 1.2.3](#)), treatment with alpelisib in combination with fulvestrant is expected to be well tolerated and it is hypothesized that it will result in delayed disease progression by inhibiting proliferation of endocrine-resistant breast cancer cells.

For further details on clinical safety, please refer to [Section 1.2.2](#) and the latest version of [Alpelisib (BYL719) Investigators Brochure].

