6.1 Study treatment

For this study, the term “investigational drug” refers to Novartis study drug alpelisib. Fulvestrant is also being used in this study. Study treatment in this study refers to the combination of drugs in each of the study arms and includes alpelisib/placebo and fulvestrant. This is a double blind placebo controlled study, the investigator and patient will be blinded (i.e. will not know if the patient is receiving alpelisib or placebo). The storage conditions for the alpelisib/placebo will be described on the medication label.

Novartis Drug Supply Management or its designee will provide alpelisib and placebo as 50 mg and 200 mg tablets as individual patient supply, packaged in bottles. Alpelisib will be dosed on a flat scale of mg/day and not be adjusted to body weight or body surface area.

Fulvestrant will be procured locally according to local practice and regulation, or supplied by Novartis (or its designee). Storage conditions are described in the medication label. Medication labels will comply with the legal requirements of each country and be printed in the local language.

All dosages prescribed and dispensed to the patient and all dose changes during the study must be recorded on the Dosage Administration Record Case Report Form (CRF).

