7.1.3 Discontinuation of study treatment

Patients may voluntarily discontinue from alpelisib/placebo and/or fulvestrant for any reason at any time. If a patient decides to discontinue from the study treatment, the investigator must make every effort (e.g. telephone, e-mail, letter) to determine the primary reason for this decision and record this information in the patient's chart and on the appropriate CRF pages. They may be considered withdrawn if they state an intention to withdraw, fail to return for visits, or become lost to follow-up for any other reason.

The investigator should discontinue alpelisib/placebo and/or fulvestrant for a given patient if, she/he believes that continuation would be detrimental to the patient's well-being.

For patients who discontinue treatment for reasons other than documented disease progression, death, lost to follow-up, or withdrawal of consent, tumor assessments must continue to be performed every 8 weeks during the first 18 months, every 12 weeks until 36 months, then as clinically indicated until documented disease progression, death, lost to follow-up, or withdrawal of consent.

Study treatment must be discontinued under the following circumstances:

- Adverse event or laboratory abnormalities as indicated in [Section 6.3](#).
- Pregnancy
- Lost to follow-up
- Physician decision
- Subject/guardian decision
- Death
- Progressive Disease
- Study terminated by sponsor
- Technical problems
- Use of prohibited treatment and medications refer to [Section 6.4.3](#) and [Section 14.2](#).
- Any other protocol deviation that results in a significant risk to the patient's safety

The appropriate personnel from the site and Novartis will assess whether alpelisib/placebo plus fulvestrant treatment should be discontinued for any patient whose treatment code has been broken inadvertently for any reason.

Patients who discontinue only one of two medications (fulvestrant or alpelisib/placebo) should NOT be considered withdrawn from the study. They should continue taking fulvestrant only or alpelisib/placebo only (as applicable) as per investigators' clinical judgment, and return for the assessments indicated in [Table 7-1](#).

If they fail to return for these assessments for unknown reasons, every effort (e.g. telephone, email, letter) should be made to contact them as specified in [Section 7.1.8](#).

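### After fulvestrant is permanently stopped, Protocol 6.3.1.2 lets blinded alpelisib/placebo run to study completion where other sections stop at progression, and no section addresses the control patient left on placebo alone

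*Protocol*

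**What the plan says.** Section 6.3.1.2 sets the trigger: "If fulvestrant is held for more than 35 days since a planned injection, then fulvestrant should be permanently discontinued". The next sentence covers the other component: "The patient may continue on alpelisib/placebo at the discretion of the investigator until study completion", with scheduled assessments carrying on.

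Two other sections also permit a single component to continue. Section 6.1.2 says that a patient who stops one drug for a reason other than progression "may continue the other study drug as part of the trial therapy at the investigators discretion until disease progression, unacceptable toxicity, death" or discontinuation for another reason. Section 7.1.3 says of patients who stop one of the two drugs: "They should continue taking fulvestrant only or alpelisib/placebo only (as applicable) as per investigators' clinical judgment".

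On when treatment ends, 6.1.5 states: "Patients will be treated until disease progression (radiologically documented according to RECIST 1.1) or until discontinuation of study treatment due to any other reason". Section 7.1.2 also ends treatment at progression. Section 7.1.3 introduces a list with "Study treatment must be discontinued under the following circumstances", and progressive disease is on that list.

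On blinding, 6.1 says that "the investigator and patient will be blinded (i.e. will not know if the patient is receiving alpelisib or placebo"; 6.5.3 keeps both blinded until study closure is being prepared. On benefit to participants, 2.6.1 says: "All patients enrolled in this trial will receive an active endocrine therapy for their disease".

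**The concern.** These are treatment instructions that a site would follow. A site reading 6.3.1.2 alone would find a different end point from a site reading 6.1.2 or 7.1.3.

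The two single-drug situations are also not alike. If alpelisib/placebo is stopped, fulvestrant remains in both arms. If fulvestrant is stopped, one arm keeps alpelisib and the other keeps only an inert tablet. Because the tablet is blinded, the investigator who decides on continuation cannot tell which of the two applies. None of the three permissive passages mentions this. At stake are the safety of those control patients and the consistency of what participants and sites are told.

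**Working it through.** No arithmetic settles this point. The check is to set the passages side by side.

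| Protocol section | What it governs | End point given |
|---|---|---|
| 6.3.1.2 | alpelisib/placebo after fulvestrant is permanently stopped | study completion |
| 6.1.2 | either drug after the other is stopped | progression, toxicity, death or another reason |
| 6.1.5 | study treatment in general | RECIST progression or another reason |
| 7.1.2 | study treatment in general | progression, among other reasons |
| 7.1.3, stop list | study treatment in general | progression is a mandatory stop |
| 7.1.3, single drug | either drug alone | none stated; clinical judgment |

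**Step 1: is 6.3.1.2 the odd one out?** Yes. Every other section that names an end point includes progression. Only 6.3.1.2 does not.

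**Step 2: can the term study completion be read so that the conflict disappears?** Three places bear on it.
- Section 7.1.6 asks for the reason for study completion to be recorded when a patient reaches progression, death, loss to follow-up or withdrawal from efficacy follow-up. That is a patient-level use, and under it the conflict nearly vanishes.
- Section 4.3 defines a patient's end of study by permanent discontinuation of study treatment plus end-of-trial procedures. Put into 6.3.1.2, this is circular: the patient continues treatment until treatment ends.
- Section 11.5 equates study completion with the last patient's last visit. Under that use the end point belongs to the whole trial.

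The readings are far apart. Section 4.3 ties the end of the trial to the final OS analysis or an earlier significant OS result. Sections 10.7.2 and 10.9 place the final OS analysis at about 54 months from the first patient randomized; the interval is shorter for patients who entered later. Section 10.8 assumes a control median PFS of 7.0 months in the mutant cohort.

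**Step 3: does any passage exclude or mention placebo alone?** No. Sections 6.1.2, 6.3.1.2 and 7.1.3 all refer to alpelisib/placebo or to the other study drug, without distinguishing the arms. Under the blind they could not do so for an individual patient.

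**Step 4: what does the SAP report?** SAP 3.6.4 summarizes permanent discontinuations and their reasons separately for each drug, and SAP 3.6.1 gives duration of exposure to each drug. Neither shows how many patients stayed on alpelisib/placebo after fulvestrant ended, or for how long.

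**The case against.** The strongest reply is that 6.3.1.2 contains one loosely worded clause. The stop list in 7.1.3 is mandatory, several sections end treatment at progression, and 7.1.6 supports a patient-level reading. This carries weight: a reader might infer that the protocol authorizes treatment beyond progression, and the documents taken together do not support that. It does not remove the conflict, because 11.5 gives the same term a trial-level meaning and 6.3.1.2 does not refer to the stop list.

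It can also be said that the investigator is not wholly in the dark. Fulvestrant is not blinded, allocation is 1:1, continuation is discretionary, patient or investigator may stop at any time, and imaging continues on schedule. That stands and limits the hazard. Still, the protocol leaves the investigator to work out that placebo alone is possible.

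A reader might see a second conflict between *may* in 6.1.2 and 6.3.1.2 and *should* in 7.1.3. The sentence in 7.1.3 is qualified by clinical judgment, so all three are discretionary.

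A reader might also infer that 2.6.1 is plainly contradicted. It is not: every patient is assigned fulvestrant from Cycle 1 Day 1, and 2.6.1 gives no duration. The tension arises only once fulvestrant has been stopped.

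**Conclusion.** The point holds as a conflict between operative instructions, together with a situation that the protocol leaves unaddressed. It rests on the wording alone and needs no assumption about how often fulvestrant is stopped by itself. Its reach is any patient who permanently stops fulvestrant and stays on the blinded component; for placebo alone, it is the control patients among them. The documents do not say how many that would be.

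A reader might go further and infer that time on placebo alone biases PFS in favour of alpelisib or inflates the type I error. The documents do not support that step. They give neither a rate of fulvestrant-only discontinuation nor a hazard after stopping. Placebo is inert, so any direct loss of effect comes from stopping fulvestrant, whether or not the tablet continues. The fulvestrant half-life of 40 to 50 days (Protocol 1.2.1.1) also argues against an abrupt change. Analysing these patients as randomized, without censoring at treatment discontinuation, is the declared approach (Protocol 10.1.1, SAP 3.8.1.1). No change to the primary analysis follows.

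Nor does a sensitivity analysis that excludes these patients follow. It would select on a post-randomization event that requires remaining on treatment long enough to qualify, and it could introduce bias of its own.

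**What to change.** 1. Reconcile Protocol 6.1.2, 6.1.5, 6.3.1.2, 7.1.2 and 7.1.3 so that they state one rule, with one end point, for alpelisib/placebo after fulvestrant is permanently discontinued. If the term study completion is kept, define it.
2. Have that rule address explicitly that a control patient may be on placebo alone, and align 2.6.1 with it. Which rule applies is for the sponsor's clinical team; none is proposed here.
3. Optionally, add to SAP 3.6.4 a by-arm count of patients who continued alpelisib/placebo without fulvestrant, and their time on it. The SAP already has the dates: time can run from the last date of exposure to fulvestrant to the last administration of alpelisib/placebo (SAP 2.1.6), where that difference is positive. For a stop on or after Cycle 2 Day 1, the last date of exposure is the last injection plus 27 days, unless death or loss to follow-up comes first.

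The cost is wording in about six places in the protocol and, if wanted, one descriptive table from dosing records already collected. No new data, test or change to the primary analysis is needed.
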